6. DATA ANALYSIS AND MANAGEMENT*

Statistical Procedures and Power Analysis.

Study design will allow systematic quantification (mean and variance) of the effects of NEATCap device and SVS mattress on automatic function, such as breathing (IBI), cardiac rhythm (R-R), frequency and duration of body movements (e.g., defined via streamlined video, artifact in pulse-oximeter plethysmographic activity, and actigraph count), blood oxygenation (e.g., durations<85%), skin temperature, and sleep states. Analyses will be conducted to determine whether interventions impinge on neural oscillators that drive breathing and cardiac control, and whether NEATCap device reduces dangerous levels of environmental noise, to improve autonomic function and sleep activity.

NCT03881553 Study Protocol and Statistical Analysis Plan

Signal processing algorithms will be used to characterize separately the instability of physiological signals, such as respiration and heartbeat. We will explore, for example, whether different durations of movement periods (e.g., 1.5-5 sec; >5 sec; >10sec) have unique relationships with withdrawal (NAS or iatrogenic) or prematurity, and are affected differently with different interventions (NEATCap device and SVS Mattress).

Parametric tests will be used for analyses of all continuous variables. The Friedman's and Wilcoxon signed-rank tests will be used for nonparametric analyses. For analyses of parametric data separate repeated measures ANOVAs will test effects of stimulus condition (ON or OFF) and trial order. Post-hoc pairwise t-tests will determine differences in responses for conditions of stimulation ON and OFF. For example, separate repeated measures ANOVAs will test effects of stimulus condition (ON or OFF) and trial order on physiological variables. Time of intervention (e.g., infant age, severity of NAS) will be a covariate to assess whether there are critical periods in infant development for optimizing the intervention as a therapeutic strategy. Pearson product-moment correlation coefficient analysis will be used to establish associations between breathing stability (IBI variance) and movement duration, with the expectation that greater variance in respiratory parameters will be positively correlated with excessive movement. *P* values of <0.05 will be considered significant.

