The number of periods and duration of intervention will not always be the same for each study session. The proposed study will test if different modes (NEATCap; Mattress SVS) affects duration of the interfeed interval, improves autonomic function, and promotes sleep. This is a within-subjects design, so all subjects will receive intervals of routine clinical care in addition to the assigned intervention/s complementary to routine care. Intervention assignment for study session is based on equipment availability, research personnel availability; it will not be determined by the subject's treating physician.

- It is possible that a subject does not receive an intervention (participate in a study session) after enrollment if: 1) We have technical difficulties and are unable to conduct studies; 2) Subject is discharged before being entered into an intervention stimulation session; 3) Doctor treating child requests we terminate the study – we will heed to the discretion of the Attending Physician or primary medical caregiver for decisions regarding termination of an infant from the study for example due to sickness, sepsis or exacerbated withdrawal symptoms (e.g., seizures) – such population of subjects will likely already be excluded by the exclusion criteria, but others unknown at this time may also ensue. Medical criteria for terminating a subject from the study will be determined by the medical caregiver treating the infant. Authorized parent, nurse or investigator may stop/postpone a study session for reasons such as excessive symptomatology preventing ability to properly study the subject (e.g., unable to keep sensors in place, infant needs to be held incessantly, skin rash), parent has visitors or simply doesn't want an infant/child studied on a particular day – this would not result in termination from the study per se. If we find that a mode of stimulation appears to make the infant/child irritable (e.g., excessive waking, crying, movement), we will end the study session for that day. If this happens on a second study-session day, we will discontinue study.

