7. PROVISIONS TO MONITOR THE DATA TO ENSURE THE SAFETY OF SUBJECTS*

NCT03881553 Study Protocol and Statistical Analysis Plan

An independent medical safety monitor will review serious adverse events reported to the IRB and will summarize each in a written report that will be submitted to the Center for Advancing Point of Care Technologies (CAPCaT) for any required reporting to NIH.

This research does not involve more than minimal risk to subjects. While it may be difficult to determine whether NEATCap or SVS mattress causes worsening of physiological function or is related to common system dysregulation of the subject, a study may be discontinued at any time if the investigators or the subject's medical caregiver suspects there are any adverse effects on breathing, heart rate, thermoregulation, oxygenation, movement or any other function.

Nurses are instructed to provide routine care and to intervene as they would typically do, e.g., in the event of a prolonged apnea, bradycardia or blood-oxygen desaturation, despite the presence of an investigator by the subject's bedside. The protocol may be ended if intervention is associated with noticeable exacerbation of irritability including disproportionate awakening, cardio-respiratory instabilities, and/or excessive rise in temperature as observed by a medical caregiver, researcher, or parent at bedside during a study session. Parent/Guardian or medical staff may terminate the study (subject withdrawn) or request not to part-take in any procedure/s at any time (subject remains in study). Our studies are conducted at the bedside so we are in frequent contact with the clinical staff; we will routinely seek informal feedback from the medical-care staff to ensure the safety of our study protocols. The medical-care staff and parent/guardian are encouraged to call us if they have any specific concerns throughout the study enrollment.

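### Sessions can be stopped because of waking or movement during ON, which overlap the outcomes, and the planned ON/OFF tests do not handle the resulting incomplete sessions

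*Combined protocol and SAP*

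**What the plan says.** Three parts of the combined protocol and SAP bear on this point.

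- **Stopping tied to stimulation (section 6).** If "a mode of stimulation appears to make the infant/child irritable (e.g., excessive waking, crying, movement), we will end the study session for that day". The next sentence adds: "If this happens on a second study-session day, we will discontinue study". Section 7 has a broader, permissive clause: "The protocol may be ended if intervention is associated with noticeable exacerbation of irritability including disproportionate awakening, cardio-respiratory instabilities"; a rise in temperature is also listed there.
- **Stopping not tied to stimulation (section 6).** "Authorized parent, nurse or investigator may stop/postpone a study session for reasons such as excessive symptomatology preventing ability to properly study the subject". This can happen in either condition.
- **Outcomes and tests (section 6).** The outcomes include "frequency and duration of body movements (e.g., defined via streamlined video, artifact in pulse-oximeter plethysmographic activity, and actigraph count" and sleep states, and the study tests whether each device "improves autonomic function, and promotes sleep". On the analysis: "For analyses of parametric data separate repeated measures ANOVAs will test effects of stimulus condition (ON or OFF) and trial order". Friedman's and Wilcoxon signed-rank tests are named for nonparametric work, and post-hoc pairwise t-tests for ON against OFF. Section 6 also says that the number and length of periods will differ between sessions.

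Nothing in the documents says whether a stopped session, the ON period that triggered the stop, or a discontinued child stays in the analysis. No report of irritability stops is planned; the review by the safety monitor in section 7 covers serious adverse events, and an irritability stop need not be one.

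**The concern.** The irritability rule acts on the child's response while the device is on, and two of its example triggers, waking and movement, are close to what the study measures. A session that goes badly during ON therefore has fewer later periods than one that goes well. The judgement is also made with the condition known, because study staff fit the cap or switch the mattress controller themselves (section 4).

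In their standard form, repeated measures ANOVA by condition and trial order and Friedman's test both need complete blocks. If they are run that way, the sessions with the worst ON responses leave the comparison. Other ways of handling the same sessions bias the estimate differently. Two things are at stake: the size and sign of any bias would rest on a choice that could be made after the data are seen, and poor tolerance of a device, a result in its own right, might not be reported.

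**Working it through.** The plan gives no sample size, effect size, SD or stopping rate, so there is no figure of its own to reproduce. The check is a simulation of direction and rough size.

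**Inputs from the documents.** Sessions average 8-12 hours, and periods follow care intervals of roughly 3-4 hours (section 4). That gives between 8/4 = 2 and 12/3 = 4 periods per session. Significance is P < 0.05 (section 6). Sidedness is not stated; two-sided is assumed, so the nominal error rate in favour of the device is 2.5%.

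**Assumptions, none from the documents.**

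- Each session runs OFF-ON-OFF-ON, with one session per child and 20 or 40 sessions.
- There is one movement score, higher being worse: y = child effect + period effect + δ·(ON). Both SDs are 1, so the correlation between periods is 1/(1+1) = 0.5.
- The session stops after the first ON period with y > √2·z(1−q), a level that an ordinary period exceeds with probability q = 2%, 5% or 10%. The thresholds are 1.414 × 2.054 = 2.90, 1.414 × 1.645 = 2.33 and 1.414 × 1.282 = 1.81.
- The test is a paired t-test on session means, ON minus OFF. Negative values favour the device.

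**Results with no true effect (δ = 0).**

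| | q = 2% | q = 5% | q = 10% |
|---|---|---|---|
| Sessions stopped | 4% | 9% | 17% |
| Complete sessions only: mean difference | -0.03 | -0.07 | -0.12 |
| – false positives for device, 20 sessions | 3.5% | 3.9% | 6.6% |
| – false positives for device, 40 sessions | 3.7% | 5.9% | 9.9% |
| Partial sessions kept, triggering period dropped | -0.04 | -0.07 | -0.14 |
| Partial sessions kept, triggering period averaged in | +0.02 | +0.04 | +0.06 |

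In the last row, false positives for the device are 1.1-2.2%. The lower limit of +0.01 in the summary range allows for variation between simulation runs at the lowest stopping rate.

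**Results with true harm (δ = +0.30, 40 sessions).** Power to detect harm is about 46% without stopping. With complete sessions only it falls to 34%, 23% and 13% as q rises. With the triggering period averaged in it is 48%, 51% and 57%, because the estimate is inflated.

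**Is the ON-only trigger the cause?** When the same rule is applied to ON and OFF periods alike (q = 5%, 20 sessions), the complete-session estimate is about 0.00. When children differ in their response to ON (SD 0.7, mean 0, 20 sessions), the complete-session bias grows to about -0.07, -0.15 and -0.23.

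**Does a mixed model repair it?** A random-intercept likelihood model (variances taken as known) was fitted to all recorded periods:

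| | Truth 0 | Truth +0.30 |
|---|---|---|
| Complete sessions only | -0.032 to -0.112 | +0.256 to +0.146 |
| Mixed model, triggering period kept | -0.001 to +0.003 | +0.297 to +0.303 |
| Mixed model, triggering period dropped | -0.047 to -0.175 | +0.233 to +0.063 |

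The model recovers the truth only if the triggering period stays in.

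**The case against.** The strongest reply is that the plan never says that incomplete sessions are dropped. Period counts vary by design, so the investigators must already average within condition, select periods or use a flexible model. The pairwise t-test and the Wilcoxon test need only one ON/OFF pair, and a session stopped in its first ON period after an OFF period supplies one. This stands. A reader might infer that the stated tests overstate benefit whatever is done, but the documents do not support that, since averaging in the triggering period moves the estimate the other way.

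Four other tempting inferences also fail:

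- *Only the minutes before the reaction are kept.* The reaction prompts the stop, and recording is continuous (section 4), so the reaction is in the data.
- *OFF periods have no matching loss.* The general clause in section 6 allows stops in either condition, which dilutes the asymmetry.
- *Every trigger is an outcome.* Crying is not listed as one.
- *Sections 6 and 7 contradict each other on whether stopping is mandatory.* One is a specific session rule and the other a permissive clause about the protocol. They can coexist, and no count of lost data has been shown to depend on the difference.

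The size is also conditional. In a simpler set-up with one ON/OFF pair per child and correlation 0.5, losing 2% of pairs gives a bias of about 0.02 SD and a two-sided type I error of 5.0-5.1%. A child may have up to four sessions, so one stopped session need not remove the child.

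None of this supplies a rule for stopped sessions, and each simple handling tried with ON-triggered stopping gave a biased estimate.

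**Conclusion.** The concern holds in a conditional form. Stopping depends on outcome values during ON, and the named tests do not deal with it. Complete-block analysis favours the device, by about -0.03 to -0.12 period SD when 4-17% of sessions stop, with false positives for the device of about 4-10% against a nominal 2.5%. Simple averages that keep the triggering period lean slightly against it, by about +0.01 to +0.06.

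These figures rest on an assumed session pattern, variance split and stopping rate, on 20 or 40 sessions, and on one session per child. The loss of a child after a second event was not simulated. If stops are rare, or fall in both conditions, the bias is small. The documents do not establish that the study's result will favour the device. They leave its direction open to an unwritten choice, and that is reason enough to amend the analysis.

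**What to change.** Change the analysis only; the stopping rule stays with the clinical team.

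1. Keep all recorded data up to and including the triggering period.
2. Replace complete-block ANOVA and Friedman's test as the main ON/OFF analysis with a mixed model on all periods: random effects for subject and session, fixed effects for condition and trial order.
3. Record the reason for each stop, and report irritability stops and discontinued children by device and condition.
4. Add a sensitivity analysis that gives the stopped ON period the worst rank in a signed-rank test. It is needed because the mixed model is unbiased only if stopping depends on recorded values, and some stops will rest on bedside impressions that are not recorded.

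The cost is SAP wording, a little more analysis work and one field on the log sheet. Section 4 already has staff log the timing and mode of conditions, but it does not specify a stop reason.

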7. PROVISIONS TO MONITOR THE DATA TO ENSURE THE SAFETY OF SUBJECTS*

NCT03881553 Study Protocol and Statistical Analysis Plan

An independent medical safety monitor will review serious adverse events reported to the IRB and will summarize each in a written report that will be submitted to the Center for Advancing Point of Care Technologies (CAPCaT) for any required reporting to NIH.

This research does not involve more than minimal risk to subjects. While it may be difficult to determine whether NEATCap or SVS mattress causes worsening of physiological function or is related to common system dysregulation of the subject, a study may be discontinued at any time if the investigators or the subject's medical caregiver suspects there are any adverse effects on breathing, heart rate, thermoregulation, oxygenation, movement or any other function.

Nurses are instructed to provide routine care and to intervene as they would typically do, e.g., in the event of a prolonged apnea, bradycardia or blood-oxygen desaturation, despite the presence of an investigator by the subject's bedside. The protocol may be ended if intervention is associated with noticeable exacerbation of irritability including disproportionate awakening, cardio-respiratory instabilities, and/or excessive rise in temperature as observed by a medical caregiver, researcher, or parent at bedside during a study session. Parent/Guardian or medical staff may terminate the study (subject withdrawn) or request not to part-take in any procedure/s at any time (subject remains in study). Our studies are conducted at the bedside so we are in frequent contact with the clinical staff; we will routinely seek informal feedback from the medical-care staff to ensure the safety of our study protocols. The medical-care staff and parent/guardian are encouraged to call us if they have any specific concerns throughout the study enrollment.

- *Confidentiality and Data Management:* In all research records, reports and publications of the study data (including medical history and physiological signals) de-identified alpha-numeric study code will identify the subject. This code will be kept in a central database on a password protected PC. Username and password are required to unlock all research-related computers; additional passwords are used for files containing the study code that identify the subjects and de-identified data files. Only research study staff will have access to the identifying file. Any hard-copy data will identify subjects only by study code, and will be kept in a locked file cabinet. We may share de-identified data with other collaborating investigators, individuals or companies/entities in order that they may assist us with signal processing, analysis and interpretation. The authorized parent/guardian may choose to have the research data anonymized at any time of the study; it will not be possible to destroy data that has already been used in analyses and data for investigational devices is required to be maintained under FDA regulations.

To help protect subject privacy, a *Certificate of Confidentiality* (COC) has been issued by the National Institutes of Health in accordance with NIH COC Policy ([NOT-OD-17-109](https://grants.nih.gov/grants/guide/notice-files/NOT-OD-17-109.html); see <https://grants.nih.gov/grants/guide/notice-files/NOT-OD-17-109.html>; and https://grants.nih.gov/grants/policy/nihgps/html5/section_4/4.1.4_confidentiality.htm). With this Certificate, researchers cannot be forced to disclose information that may identify a study subject, even by a court subpoena, in any federal, state, or local civil, criminal, administrative, legislative, or other proceedings. This Certificate allows the

NCT03881553 Study Protocol and Statistical Analysis Plan

researchers to resist demands for identifying information with the following exceptions: 1) The Certificate does not prevent investigators from mandate reporting to health officials certain communicable diseases required by state law or local law; 2) The Certificate does not prevent investigators from reporting to authorities any knowledge of child or elder abuse, and/or intent to hurt oneself or others. The Certificate cannot be used to resist a demand for information from the US Government that is used to audit or evaluate federally funded projects. There is also information that must be disclosed to the FDA. Infants at risk for NAS due to exposure to drugs *in utero* are identified to the study investigators by physicians treating the infants. The infant's medical team is responsible for relevant mandatory reporting.
